5.1.3.3 Survival Follow-up Period

In parallel with the safety follow-up period, participants in Parts 1A, 1B, 2A and 2B will start the survival follow-up period. Participants will be followed-up by telephone every 12 weeks (from EOT) for 2 years until death, loss to follow-up, withdrawal of consent, or conclusion of the study, whichever comes first. Participants with SD, PR or CR will have both the response follow-up period and survival follow-up period occur simultaneously during the 2-year follow-up period. The duration of this follow-up is up to 2 years following the last dose of study drug, although a longer follow-up period could be considered in selected cases if an efficacy signal is apparent. Tumor assessment scans, for participants who have ongoing clinical benefit beyond the 2 year period following last dose of study drug, may continue to be collected as part of standard-of-care treatment.

In Parts 1C and 2C, the survival follow-up period will continue for 2 years following the last dose of study drug or until death, lost to follow-up, withdrawal of consent, or conclusion of the study, whichever comes first. Survival follow-up visits will occur every 12 weeks (\pm 7 days) until 2 years after the last dose of study drug. Study assessments are to be collected as outlined in [Table 2-5](#).

5.1.3.4 Retreatment During Follow-up Periods (Parts 1A, 1B, 2A, and 2B)

Retreatment may be allowed for participants with disease progression during the safety, response or survival follow-up period. Participants completing approximately 3 cycles of study therapy (or up to a maximum of 6 cycles, if applicable), and entering the survival follow-up period with

ongoing disease control (CR, PR or SD), may be eligible for retreatment upon disease progression. Eligibility will be dependent upon participants having confirmed disease progression within 12 months after the last dose of study drug, and will be considered on a case by case basis, after careful evaluation and discussion with the BMS Medical Monitor, to determine whether the risk/benefit ratio supports administration of further study therapy. Participants meeting criteria for retreatment will have to provide written consent prior to receiving any additional retreatments, by signing an ICF which describes any reasonably foreseeable risks or discomforts, or other alternative treatment options. Participants meeting criteria for, and consenting to, retreatment, will be treated with the originally assigned monotherapy or combination therapy regimen (eg, same dose and dose schedule as administered during the first 24 weeks), unless that dose and its schedule were subsequently found to exceed the MTD. In that case, the participant will be treated at the next lower or alternate dose and schedule. Alternatively, if the MTD has been determined at the time point when the participant is being retreated, that participant can be retreated at the MTD.

Participants entering retreatment will follow the same Time and Events schedule as outlined in [Section 2](#). Samples for PK will be collected less frequently (only at predose of each treatment cycle).

5.1.4 *Treatment Beyond Progression*

Treatment beyond progression may be allowed for a maximum treatment duration of up to 2 years in selected participants with initial RECIST v1.1 progressive disease, following discussion and agreement with the BMS Medical Monitor that the benefit-risk assessment favors continued administration of study treatment (eg, participants are continuing to experience clinical benefit, as assessed by the Investigator, tolerating treatment, and meeting other criteria).

As described in [Section 5.4.6](#), accumulating evidence indicates a minority of participants treated with immunotherapy may derive clinical benefit despite initial evidence of progressive disease. Participants will be permitted to continue on study drug for treatment beyond initial RECIST v1.1-defined progressive disease as long as they meet the following criteria:

- Investigator-assessed clinical benefit and no rapid disease progression
- Participant is tolerating study treatment
- Stable performance status
- Treatment beyond progression will not delay an imminent intervention to prevent serious complications of disease progression (eg, CNS metastases)
- Participant provides written informed consent prior to receiving additional BMS-986207, nivolumab, and ipilimumab treatment, using an ICF describing any reasonably foreseeable risks or discomforts, or other alternative treatment options.

The decision to continue treatment beyond initial Investigator-assessed progression should be discussed with the BMS Medical Monitor and documented in the study records. A follow-up scan should be performed within 4 to 6 weeks of original progressive disease to determine whether there has been a decrease in the tumor size or continued progression of disease. Subsequent scans should be performed every 12 weeks until further progression is determined. If the Investigator

feels that the participant continues to achieve clinical benefit by continuing treatment, the participant should remain on the trial and continue to receive monitoring according to the Schedule of Activities in [Section 2](#). For participants who continue study therapy beyond progression, further progression is defined as an additional 10% increase in tumor burden from time of initial progressive disease. This includes an increase in the sum of diameters of all target lesions and/or the diameters of new measurable lesions compared to the time of initial progressive disease. Nivolumab, ipilimumab, and BMS-986207 treatment should be discontinued permanently upon documentation of further progression.

New lesions are considered measurable at the time of initial progression if the longest diameter is at least 10 mm (except for pathological lymph nodes which must have a short axis of at least 15 mm). Any new lesion considered non-measurable at the time of initial progression may become measurable and therefore included in the tumor burden if the longest diameter increases to at least 10 mm (except for pathological lymph nodes, which must have a short axis of at least 15 mm). In situations where the relative increase in total tumor burden by 10% is solely due to inclusion of new lesions which become measurable, these new lesions must demonstrate an absolute increase of at least 5 mm.

5.1.5 Data Monitoring Committee and Other External Committees

BMS has developed a multi-layered process to ensure safety monitoring through close collaboration of study site Investigators, the BMS study team, and the BMS Worldwide Patient Safety (WWPS)-led Safety Management Team (SMT). This collaborative process constitutes the safety-monitoring plan for the study. To support safety oversight, BMS has established ongoing processes for collection, review, analysis, and submission of individual adverse event reports and their aggregate analyses. Because this is an open-label study, WWPS, the BMS Medical Monitor, and the Investigators will have access to all data necessary for safety evaluation.

BMS WWPS is an internal group that operates independently from the clinical team to monitor safety across all BMS protocols and analyze all accumulated safety data. Within BMS, an SMT is established for investigational therapies under clinical development, and a member of WWPS chairs this team. In addition, safety signal detection is performed at least monthly and ad hoc throughout the study by the SMT composed, at a minimum, of the WPS medical safety assessment physician (Chair of the SMT) and WWPS single-case review physician, the study Medical Monitor, the study biostatistician, and epidemiologist, all of whom evaluate the safety data regularly. Furthermore, the SMT routinely monitors for actual or potential issues related to participant safety that could result in a change in the medical benefit-risk balance associated with the use of study treatment(s). For Part 2C, continuous safety monitoring based on a Bayesian framework is also planned in the NSCLC cohort for ongoing evaluation of the tolerability of the selected dose.

5.2 Number of Participants

The approximate number of evaluable participants will be approximately 241. Approximately 100 of these participants will be treated with monotherapy and combination therapy dose escalation (35 participants each for Part 1A and Part 1B and additional 30 participants for the substudy of

Part 1B), and approximately 36 participants treated (6 initial participants for safety evaluation followed by evaluation of approximately 12 additional participants per dose level) with BMS-986207, nivolumab, and ipilimumab in the Triplet Cohort (Part 1C). The remaining participants (up to 105) will be treated as part of dose expansion, with up to 24 participants in Part 2A and 41 participants in Part 2B, and 40 participants with NSCLC and [REDACTED]

[REDACTED] (pre-existing or prior PD-L1 IHC results from testing of tumor tissue) considered to be response-evaluable, in Part 2C. In the event more than 25% of the participants in Part 2C are found to have a PD-L1 tumor cell score of < 1%, based on central lab testing, additional participants may be enrolled in order to have at least 30 participants with a PD-L1 tumor cell score $\geq 1\%$.

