cycles of 8 weeks. Following each treatment cycle, the decision to treat a participant with additional cycles of study therapy (up to a maximum of 6 cycles), will be based on tumor assessment at the end of each cycle. In Parts 1C and 2C, nivolumab and BMS-986207 will be administered every 3 weeks and ipilimumab will be administered every 6 weeks until progression, unacceptable toxicity, or other reasons specified in the protocol for up to 2 years.

Each monotherapy treatment cycle will comprise 4 doses of BMS-986207 administered every 2 weeks (q2w) or 2 doses of BMS-986207 every 4 weeks (q4w) in Part 1A and 2A. BMS-986207 infusions will take place over 60 minutes and will require a 60 minute observation period after all infusions in Cycle 1 for each participant. For participants < 42 kg on the 1600 mg dose, the infusion time will be longer than 1 hour. In Parts 1B and 2B, each combination treatment cycle will comprise 4 doses of BMS-986207 administered q2w or 2 doses of BMS-986207 when administered q4w, each dose administered with nivolumab. In Part 1B and 2B, when both study drugs are given in combination, nivolumab will be given first, over a 30-minute infusion period, followed by BMS-986207 over a 60-minute infusion period, with a 60-minute observation period after all infusions in Cycle 1 for each participant, and at least 30 minutes after completion of the infusion of nivolumab. Tumor progression and response will be assessed using RECIST v1.1 criteria for solid tumors. The study design is shown in [Figure 2](#).

The approximate number of evaluable participants will be 241. Approximately 100 of these participants will be treated with monotherapy and combination dose escalation (Part 1A and Part 1B, respectively). Approximately 36 participants will be treated (6 initial participants for safety evaluation followed by evaluation of approximately 12 additional participants per dose level) with BMS-986207, nivolumab, and ipilimumab in the Triplet Cohort (Part 1C). The remaining (up to 105) participants will be treated as part of dose expansion with up to 24 participants in Part 2A and 41 participants in Part 2B, and 40 participants with NSCLC [REDACTED] pre-existing or prior PD-L1 IHC results from testing of tumor tissue) considered to be response-evaluable, in Part 2C.

[figure not shown]
Study Design

Figure 1: Overall Study Design

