5.1.2.7 Cohort Expansion (Parts 2A, 2B, and 2C)

The purpose of cohort expansion is to gather additional safety, tolerability, preliminary efficacy, PK, [REDACTED] information regarding BMS-986207 alone and in combination with nivolumab. Continuous evaluation of toxicity events in the cohort expansions will be performed throughout enrollment in the expansion cohorts. If, at any time, the aggregate rate of treatment-related toxicities meeting DLT criteria exceeds 33% across all participants treated in cohort expansions 2A or 2B, the findings will be discussed and further enrollment will be interrupted. Depending on the nature and grade of the toxicity, and after assessing the risk/benefit ratio, a new dose for all cohorts may be initiated at a previously tested lower dose level or at a dose level intermediate to previously tested, lower dose levels.

In Part 2A, only CRC will be evaluated in cohort expansion with BMS-986207 as monotherapy. In Part 2B, the 3 disease-restricted populations, ovarian cancer, colorectal cancer (CRC) and HCC will be investigated in cohort expansions with BMS-986207 in combination with nivolumab. A Fleming 2-stage design framework will be used as a guide in cohort expansion.

During the cohort expansion phase, participants with CRC who have disease progression on BMS-986207 monotherapy will be able to cross over to combination treatment (BMS-986207 + nivolumab), once the CRC expansion arms (ie, monotherapy and combination therapy) are both enrolling. This cross-over option, for CRC participants only, is not applicable during the escalation phases.

The purpose of Part 2C is to gather preliminary efficacy information regarding BMS-986207 in combination with nivolumab and ipilimumab. Participants with advanced, treatment-naïve NSCLC whose tumors express PD-L1 will be treated with BMS-986207 in combination with nivolumab and ipilimumab. BMS-986207 will be administered at 600 mg q3w (or tolerable dose as determined in Part 1C) and nivolumab will be administered at 360 mg q3w. Ipilimumab, at a dose of 1 mg/kg, will be given q6w.

Part 2C may begin once there is sufficient safety data from a minimum of 6 participants in Part 1C.

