10.1.3.1 Cohort Expansion in Part 2A and Part 2B

Part 2A will be an expansion phase of the BMS-986207 monotherapy in participants with CRC at 1 dose level. Part 2B will be an expansion phase for BMS-986207 in combination with nivolumab in participants with CRC, HCC, and ovarian cancer. Each disease cohort expansion will be handled independently and there will be no multiplicity adjustment.

The Fleming 2-stage design framework will be used as a guide for the expansion cohorts in Parts 2A and 2B.^{42,43} The total sample size for each expansion cohort will be calculated to provide a reasonable false-positive rate (FPR) <10% and false-negative rate (FNR) < 10% based on

assumptions of true (target) and historic ORR for each indication. The assumed historic and target response rates may change over time and may need to be adjusted by the time when the response data from this study are available. The sample size and operational characteristics of using a 2-stage design, as an example, are provided in Table 10.1.3.1-1, although this is not used for statistical hypothesis testing. Using a 2-stage design provides an option to stop early for futility, as well as a signal of preliminary [REDACTED] activity for strong-go, early on. Enrollment may continue into Stage 2, while the planned number of participants for Stage 1 are followed for efficacy evaluable tumor assessments. There will be no stopping of a disease cohort for efficacy, although an early plan for the next stage of clinical development may be initiated. Sample sizes may need to be increased in order to explore differential responses between [REDACTED] expressed and nonexpressed groups.

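### Part 2B is stated as 41 participants, but its three independent cohorts as designed add up to as many as 67, so the expansion and study totals are 26 too low

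*Combined protocol and SAP*

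**What the plan says.** Section 5.2 builds the study size from its parts.

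- The overall figure reads: "The approximate number of evaluable participants will be approximately 241". The Synopsis agrees: "The approximate number of evaluable participants will be 241".
- Dose escalation is 100, made up of "35 participants each for Part 1A and Part 1B and additional 30 participants for the substudy of" Part 1B. Part 1C adds about 36.
- For expansion: "The remaining participants (up to 105) will be treated as part of dose expansion", divided "with up to 24 participants in Part 2A and 41 participants in Part 2B", plus 40 in Part 2C.

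The design sections describe Part 2B as three cohorts. Section 5.1.2.7 says: "In Part 2B, the 3 disease-restricted populations, ovarian cancer, colorectal cancer (CRC) and HCC will be investigated in cohort expansions". Section 10.1.3.1 says: "Each disease cohort expansion will be handled independently and there will be no multiplicity adjustment". It also says that the sample size is worked out for each expansion cohort, with false-positive and false-negative rates both below 10%. Table 10.3.1-1 reports ORR by treatment for each tumour type in Parts 2A and 2B.

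Table 10.1.3.1-1 has two rows for the combination with nivolumab. One covers HCC and ovarian cancer (historic 10%, target 30%; 15 at Stage 1, 26 cumulative). The other covers CRC (historic 2%, target 30%; 7 at Stage 1, 15 cumulative).

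**The concern.** The figure of 41 equals the two Part 2B table rows added once each, yet one of those rows stands for two tumour types that the text keeps separate. No section says that HCC and ovarian cancer are pooled.

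Section 10.1.3 says that the expansion size rests strictly on efficacy, so the error falls on the number the design depends on. If 41 is treated as a limit, the HCC and ovarian cohorts cannot be run with the printed stage sizes and cut-offs. If the cohorts are run as designed, enrolment can exceed the size stated in the Synopsis and Section 5.2 by a full cohort.

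**Working it through.** **Inputs.** Part sizes are from Section 5.2. Stage sizes, cut-offs and response rates are from Table 10.1.3.1-1.

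**1. Reproduce the stated totals.**

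- Part 2B: 26 + 15 = 41
- Expansion: 24 + 41 + 40 = 105
- Escalation: 35 + 35 + 30 = 100
- Study: 100 + 36 + 105 = 241

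Every stated figure is matched exactly, with the HCC/ovarian row counted once.

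**2. Check that the shared row is a design for one cohort.** For each row, the probability of early termination (PET) is P(X ≤ futility cut-off) at the historic rate. The probability of early efficacy (PEE) is P(X ≥ efficacy cut-off) at the target rate. X is binomial with the Stage 1 size.

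| Row | Stage 1 n | PET computed (stated) | PEE computed (stated) |
|---|---|---|---|
| Part 2A CRC | 11 | 80.1% (80) | 67.8% (68) |
| Part 2B HCC, ovarian | 15 | 54.9% (55) | 70.3% (70) |
| Part 2B CRC | 7 | 86.8% (87) | 67.1% (67) |

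For HCC/ovarian, PET = 0.9^15 + 15 × 0.1 × 0.9^14 = 0.549. So 15 then 26 describes a single cohort testing 10% against 30%. Two independent cohorts each need it.

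**3. Recount with three cohorts.**

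- Part 2B: 26 + 26 + 15 = 67, which is 26 more than 41 (26/41 = 63%)
- Expansion: 24 + 67 + 40 = 131, against 105
- Study: 100 + 36 + 131 = 267, against 241 (26/241 = 10.8%)

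**4. What a limit of 41 would allow.**

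- All three cohorts stop at Stage 1: 15 + 15 + 7 = 37, which fits.
- Only CRC goes to Stage 2: 15 + 15 + 15 = 45, which does not fit.
- Only one of HCC or ovarian goes to Stage 2: 26 + 15 + 7 = 48, which does not fit.

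So 41 is enough only if no cohort enters Stage 2. At the historic rates, all three stop for futility with probability 0.549 × 0.549 × 0.868 = 0.26. At the target rates the probability is 0.0353 × 0.0353 × 0.0824, about 0.0001. Both products assume independent cohorts and no enrolment beyond Stage 1 while responses are awaited. Section 10.1.3.1 in fact permits such enrolment.

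If CRC takes its 15, HCC and ovarian share 26. Their two Stage 1 samples need 30, so they cannot both complete Stage 1 under any split. With 13 each, neither does, and no single-stage cut-off meets both error limits for 10% against 30%:

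| Rule at n = 13 | False-positive rate | Power |
|---|---|---|
| ≥ 2 responses | 37.9% | 93.6% |
| ≥ 3 responses | 13.4% | 79.8% |
| ≥ 4 responses | 3.4% | 57.9% |

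The smallest single-stage size that meets both limits is 25 (≥ 5 responses: false-positive rate 9.8%, power 91.0%).

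**The case against.** The strongest reply is that these numbers are not commitments. Section 10.1.3.1 presents the two-stage design as a guide and its table as an example, allows the assumed rates to change, and foresees possible increases in size. The totals are labelled approximate. ORR is a secondary endpoint in Part 2B, and Section 3.1 says that no hypothesis is formally tested. Also, 67 is a ceiling. At the historic rates, with futility stopping, the average Part 2B size is 2 × (15 + 11 × 0.451) + (7 + 8 × 0.132), about 48.

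It is right that 67 is a maximum and should be written as such. But Section 5.2 uses Stage 2 maxima throughout: 24 for Part 2A, and 41 is itself a sum of Stage 2 sizes. The like-for-like figure is therefore 67, and even the average of 48 is above 41. A gap of one entire cohort is not rounding, especially when every other component adds exactly.

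A second reply is that the sponsor may have meant 26 across both tumour types. The documents do not show how 41 arose, so this cannot be excluded. It would, however, contradict Sections 5.1.2.7 and 10.1.3.1 and the by-tumour-type analysis in Table 10.3.1-1, so the text would still need correction.

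A third reply concerns the total. The 36 for Part 1C matches two dose levels of 18, and it is unclear whether it includes the six participants already treated at 1200 mg or any further dose level. Part 2C may also enrol extra participants after central PD-L1 testing. This stands: 267 corrects Part 2B only and carries the other parts over as stated.

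**Conclusion.** The concern holds. The Synopsis and Section 5.2 understate the maximum size of Part 2B by 26: 41 stated, 67 under the plan's own design. The same 26 carries into expansion (105 against 131) and the study total (241 against 267).

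This rests on three assumptions: HCC and ovarian cancer are separate cohorts, as the text says; the printed stage sizes are used; and the stated sizes of Parts 1A, 1B, 1C, 2A and 2C are correct.

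On the second assumption, there is a separate point that could move the 26 itself. With the printed HCC/ovarian cut-offs, the chance of an efficacy conclusion at a 30% response rate is 85.9%. That is a false-negative rate of about 14%, not the below-10% rate claimed in the table footnote.

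**What to change.** In the Synopsis and Section 5.2, state up to 67 for Part 2B (26 HCC, 26 ovarian cancer, 15 CRC), up to 131 in expansion and about 267 overall. Confirm the Part 1C and Part 2C components before printing the total. In Table 10.1.3.1-1, give HCC and ovarian cancer their own rows.

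If 41 is intended, state that HCC and ovarian cancer are pooled or name the cohort that is dropped. Then remove the independence statement from Section 10.1.3.1, and align Section 5.1.2.7 and Table 10.3.1-1.

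The first route only corrects stated totals, because Section 10 already implies the larger number. The second changes the design description and would need its operating characteristics restated for the pooled or reduced set of cohorts.

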7.2 Method of Treatment Assignment

In this open-label study, enrolled participants, including those not dosed, will be assigned via IRT sequential participant numbers starting with [REDACTED] (eg, [REDACTED]). Those enrolled participants meeting the inclusion criteria, and none of the exclusion criteria, will be eligible to be dosed. Sequential numbering may restart at [REDACTED] for each participating site as the distinct participant identification number will ultimately comprise of the site number and participant number, (eg, [REDACTED]). In the expansion phase only, participants with CRC will be randomized in a 1:1 manner to either BMS-986207 monotherapy, or combination therapy with BMS-986207 and nivolumab, to eliminate the possibility of enrollment bias.

Participants in Part 2C with 1L NSCLC and tumor cell PD-L1 expression of $\geq 1\%$ based on pre-existing lab results will be enrolled to receive combination therapy with BMS-986207, nivolumab, and ipilimumab. If more than 25% of the participants have a PD-L1 score < 1% as determined by the central lab, additional participants may be enrolled in order to have at least 30 participants with a tumor cell score of $\geq 1\%$.

Participants will not be replaced if they are discontinued from the study secondary to an AE unless the AE can be determined to be unrelated to treatment. If a participant is replaced after dosing, then the replacement participant will be assigned the original participant's number plus [REDACTED]. The replacement participant will receive the same treatment as the participant being replaced but a new participant number will be assigned to him or her. For example, Participant [REDACTED] would be replaced by Participant [REDACTED].

Study treatment will be dispensed at the study visits as listed in Schedule of Activities ([Section 2](#)).

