10.1.3.2 Cohort Expansion in Part 2C

Part 2C will be an expansion phase of the BMS-986207 in combination with nivolumab and ipilimumab in participants with advanced treatment-naïve NSCLC whose tumor cells express $\geq 1\%$ PD-L1.

The sample size for Part 2C is based on assessing an initial [REDACTED] activity signal as estimated by the ORR following treatment in the triplet combination arm and to provide additional information for the safety profile in the 1L NSCLC population.

One or two doses are planned to be evaluated in Part 2C and a minimum of 20 participants are enrolled per dose level of BMS-986207. So approximately 40 evaluable participants in total with 1L NSCLC with tumor cell PD-L1 expression of $\geq 1\%$ will be treated with BMS-986207 in combination with nivolumab and ipilimumab.

In the event pre-existing PD-L1 results are not confirmed by the central lab test, additional participants (up to 20%) will be enrolled to achieve a sample size of 40 evaluable participants.

The following Bayesian posterior probability (PP) criteria will be used to assess signal of anti-tumor activity with benchmark of 36% as unfavorable ORR and 56% as desirable ORR:^{44,45}

- An [REDACTED] activity signal is based on ORR satisfying the dual criteria: PP (ORR ≥ 0.56) $\geq 40\%$ and PP (ORR ≥ 0.36) $\geq 80\%$
- A lack of activity signal is based on ORR meeting the criterion: PP (ORR ≥ 0.36) $< 20\%$

A beta prior distribution beta (1, 1) for ORR and Binomial Bin (n, ORR) likelihood for number of responders were used.

Based on the above criteria, for each dose level a total of 20 evaluable participants in Part 2C will provide approximately 6.5% chance to show [REDACTED] activity when a true ORR is 36%, and at least 63% chance of showing activity signal if the true ORR is 56% or more (see [Table 10.1.3.2-1](#))

The ORR thresholds for efficacy signal (responders $\geq 11/20$) and lack of efficacy ($\leq 6/20$) and the operating characteristics of the posterior probability criteria are shown in [Table 10.1.3.2-1](#).

Table 10.1.3.2-1: Operating characteristics of criteria for antitumor activity by ORR

Sample Size	True ORR	PP (Activity)	PP (No Activity)	PP (Inconclusive)	Responder Cutoff Activity/ No Activity
20	0.3	0.017	0.416	0.566	11/6
20	0.36	0.065	0.217	0.718	11/6
20	0.5	0.412	0.021	0.567	11/6
20	0.56	0.626	0.005	0.369	11/6
20	0.6	0.755	0.002	0.243	11/6
22	0.3	0.014	0.313	0.673	12/6
22	0.36	0.058	0.14	0.801	12/6
22	0.5	0.416	0.008	0.576	12/6

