10.2 Populations for Analyses

For purposes of analysis, the populations in are defined in Table 10.2-1.

Table 10.2-1: Population for Analyses

Population	Description
Enrolled	All participants who sign informed consent and are registered into the IRT
NSCLC efficacy	All treated participants in Part 2C with PD-L1 $\geq 1\%$ by central lab
Treated	All participants who take at least 1 dose of study treatment.
Response-evaluable	All treated participants with measurable disease at baseline and one of the following: (a) at least 1 post baseline tumor assessment, (b) clinical progression, (c) death
Pharmacokinetic	All treated participants who have evaluable concentration-time data
Immunogenicity	All treated participants who have baseline and at least 1 post baseline pre-infusion immunogenicity assessment

Abbreviations: IRT, Interactive Response Technology.

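### Part 2C: the lack-of-efficacy threshold of ≤6/20 breaks its own posterior criterion, and the PD-L1 top-up rules in 5.2/7.2 and 10.1.3.2 disagree, with a modest effect on the per-dose figures

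*Combined protocol and SAP*

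**What the plan says.** **Decision rule.** Section 10.1.3.2 uses a Beta(1,1) prior. An activity signal needs PP(ORR ≥ 0.56) of at least 40% and PP(ORR ≥ 0.36) of at least 80%. "A lack of activity signal is based on ORR meeting the criterion" PP(ORR ≥ 0.36) below 20%. The sentence that opens "The ORR thresholds for efficacy signal (responders" then gives at least 11/20 for a signal and at most 6/20 for lack of efficacy. Table 10.1.3.2-1 lists the cut-offs as 11/6, 12/6, 13/7 and 14/8 for n = 20, 22, 24 and 26, with no inequality sign.

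**Operating characteristics.** The section states that "for each dose level a total of 20 evaluable participants in Part 2C will provide approximately 6.5% chance" of a signal at a true ORR of 36%, and at least 63% at 56% or more. The per-dose floor is that "a minimum of 20 participants are enrolled per dose level of BMS-986207".

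**Top-up.** Participants enter on a pre-existing PD-L1 result and are then tested centrally.
- Section 5.2, if more than 25% are centrally below 1%: "additional participants may be enrolled in order to have at least 30 participants with a PD-L1 tumor cell score" of at least 1%. Section 7.2 agrees: "additional participants may be enrolled in order to have at least 30 participants with a tumor cell score of" at least 1%.
- Section 10.1.3.2, if pre-existing results are not confirmed: "additional participants (up to 20%) will be enrolled to achieve a sample size of 40 evaluable participants". It has no 25% trigger.

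**Population.** Section 10.2 defines the NSCLC efficacy set as "All treated participants in Part 2C with PD-L1" of at least 1% by central lab. Its response-evaluable set carries no PD-L1 condition. Section 10.3.1 names the treated population for the final efficacy analysis, but limits the Part 2C ORR method to centrally confirmed participants.

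**The concern.** There are two separate problems.

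First, a printed decision threshold contradicts the criterion it should implement. A dose with exactly 6 responders of 20 would be called inactive under the sentence and inconclusive under the criterion, so two statisticians could report different calls on the same data for a primary endpoint of Part 2C.

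Second, the top-up rules differ in trigger, obligation and target. A team working only from 5.2 and 7.2 may stop with 30 to 39 confirmed; a team working from 10.1.3.2 must aim for 40. The 6.5% and 63% refer to 20 evaluable per dose, while the only per-dose minimum counts enrolled participants. If ORR is taken in centrally confirmed participants and two doses are tested, nothing in 5.2/7.2 secures that 20.

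**Working it through.** **1. Reproducing the plan's figures (10.1.3.2).** After x responders of n, the posterior is Beta(1+x, 1+n−x), so PP(ORR ≥ t) = P(Bin(n+1, t) ≤ x).
- n = 20, x = 11: PP(≥0.56) = 0.451 and PP(≥0.36) = 0.961, so both conditions hold. At x = 10, PP(≥0.56) = 0.288, which fails. The activity cut-off of 11 is right.
- P(Bin(20, 0.36) ≥ 11) = 0.065 and P(Bin(20, 0.56) ≥ 11) = 0.626, as printed.

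**2. The no-activity cut-off.** The requirement is PP(ORR ≥ 0.36) < 0.20. For 6/20: P(Bin(21, 0.36) ≤ 6) = 0.322. For 5/20: P(Bin(21, 0.36) ≤ 5) = 0.175.

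| n | Printed c | PP at c | PP at c−1 | P(X ≤ c) at ORR 36% | P(X ≤ c−1) at ORR 36% | Tabled no-activity probability |
|---|---|---|---|---|---|---|
| 20 | 6 | 0.322 | 0.175 | 0.380 | 0.217 | 0.217 |
| 22 | 6 | 0.223 | 0.111 | 0.269 | 0.140 | 0.14 |
| 24 | 7 | 0.271 | 0.148 | 0.320 | 0.182 | 0.182 |
| 26 | 8 | 0.318 | 0.188 | 0.370 | 0.226 | 0.226 |

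The tabled probabilities were therefore computed with cut-offs of 5, 5, 6 and 7. At a true ORR of 30% and n = 20, ≤6 gives 0.608, while the table (and ≤5) gives 0.416.

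**3. Confirmed participants per dose under 5.2/7.2 alone.** With exactly 10 participants treated before 1:2 randomization (5.1.2.7 says at least 10) and 40 in total, the doses receive 10 + 30/3 = 20 and 30 × 2/3 = 20. The 25% trigger is not exceeded with up to 10 of 40 unconfirmed, so as few as 30 confirmed can remain with no top-up.

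Let U of 40 be unconfirmed at random. The number K unconfirmed in one dose is hypergeometric (40, U, 20). Re-deriving the activity cut-off a(n) from the criteria at each n, the averaged chance of a signal is Σ P(K = k) × P(Bin(20−k, ORR) ≥ a(20−k)).

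Example, U = 2: the dose has 20, 19 or 18 confirmed with probabilities 0.244, 0.513 and 0.244, and cut-offs 11, 11 and 10.
- ORR 36%: 0.244×0.065 + 0.513×0.043 + 0.244×0.071 = 0.055.
- ORR 56%: 0.244×0.626 + 0.513×0.529 + 0.244×0.611 = 0.573.

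| U of 40 | Signal at ORR 36% | Signal at ORR 56% |
|---|---|---|
| 0 (as stated) | 6.5% | 62.6% |
| 2 | 5.5% | 57.3% |
| 4 | 5.8% | 56.5% |
| 6 | 6.7% | 57.1% |
| 8 | 8.4% | 59.5% |
| 10 | 10.0% | 61.4% |

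**4. The 20% allowance in 10.1.3.2.** 40 × 1.2 = 48 enrolled. 48(1−d) ≥ 40 requires d ≤ 16.7%. The documents give no discordance rate d. At an assumed 10%, 15%, 20% and 25%, the chance that 48 enrolled give at least 40 confirmed, P(Bin(48, d) ≤ 8), is 95%, 71%, 36% and 12%.

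**The case against.** **On the cut-offs.** A reader might infer that every printed no-activity cut-off is wrong, or that the table's operating characteristics are. The documents do not support either. Only 6/20 carries an at-most sign; the table column has none and, read as fewer than, meets the criterion and matches its own probabilities in all four sizes. No Part 2C futility stop hangs on the cut-off: section 10.3.8 limits Part 2C interim analyses to administration or publication. What stands is that the text sentence is wrong, and that it invites the same reading of the table.

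**On the top-up.** A reader might infer that the rules are incompatible, or that Part 2C is underpowered. Neither follows. Reaching 40 confirmed satisfies both rules. The 6.5% and 63% are stated for 20 evaluable and are correct there. The posterior criteria work at any n, so a smaller confirmed count does not leave the team without a rule or oblige it to carry over the count of 11. Single values of n can look alarming (13.0%/68.2% at n = 15), but much of that is binomial saw-tooth: n = 21, above plan, gives 3.9%/54.9%. No hypothesis is formally tested (3.1), and a single dose with 30 confirmed exceeds 20.

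**On the population.** If ORR were analysed in all treated participants, as the opening of 10.3.1 could be read, the enrolment minimum would supply 20 per dose, apart from anyone enrolled but not treated. The 5.2 text describing the 40 is partly blacked out, so what it says about PD-L1 cannot be fully read. This makes the size conditional; it does not remove the mismatch between the legible rules.

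**Conclusion.** The threshold of at most 6/20 is wrong as written: it has a posterior probability of 0.322 against a limit of 0.20, and it raises the chance of a no-activity call from 0.217 to 0.380 at ORR 36%. This rests on the plan's own prior and criterion and needs no outside assumption.

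The top-up conflict is real in the current text, but its consequence is modest. Relative to the stated figures, the averaged per-dose chance of a signal moves by at most about 3.5 points at ORR 36% (10.0% against 6.5%) and about 6 points at ORR 56% (56.5% against 62.6%). The direction at 36% is mixed. These sizes assume ORR in centrally confirmed participants, two doses, a 20/20 split, 2 to 10 of 40 unconfirmed at random, and criteria applied at the actual n. The supportable statement is that 6.5% and 63% are not secured, not that they are lost.

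**What to change.** 1. In 10.1.3.2, change the lack-of-efficacy threshold to ≤5/20. In Table 10.1.3.2-1, either print ≤5, ≤5, ≤6 and ≤7 or label the no-activity column as fewer than. The tabled probabilities stay as they are. Cost: one sentence and one column or its header.
2. Use one trigger and one target in 5.2, 7.2 and 10.1.3.2.
3. State whether the 20 per dose and the 40 in total are centrally confirmed, and make that agree with the Part 2C ORR population in 10.2 and 10.3.1.
4. If the floor of 30 is kept, say that the posterior criteria are applied at the actual confirmed n per dose and that 6.5% and 63% hold only at n = 20.
5. If the target of 40 is kept and means centrally confirmed, say what happens when 48 enrolled give fewer than 40.

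Items 2 to 5 are wording only. They need no participants beyond those 10.1.3.2 already allows, and no large added tables.
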